**Table 2. Power calculation for primary outcomes between water and NSB arms**

Outcome type	Outcome	Mean change	SD	Correlation	N	Alpha*	Power (Beta)	N (corrected for 20% loss to follow up)
Primary outcomes family								

Primary	Microbiome UniFrac Distance	0.04	0.07	0.7	60	0.0375	98%	75
Primary	Glucose iAUC	44.81 mmol/L/min (20%)	113 mmol/L/min	0.7	60	0.025	89%	75

P-value order will be from largest to smallest.

**10.05 Recruitment.** Participants will be recruited through postings and flyer handouts at St. Michael's Hospital, the University of Toronto, local clinics, and surrounding areas, advertisements in newspapers and on transit, and online listings on Craigslist and Kijiji. Some participants will complete a Survey Monkey to assess general eligibility. We will be utilizing a digital marketing group, TrialFacts, to launch a campaign to recruit participants. TrialFacts works exclusively with research groups to provide specialized patient recruitment services for clinical trials. Participants will be screened first by telephone. Eligible participants will be called in for an information session on the study including being provided the consent form. Those that wish to participate will provide written consent and will subsequently have an in-person screening including blood work. Based on our most recent FACE trial (NCT02459834), we estimate a recruitment rate of 1-2 participants/week and therefore plan to recruit all the participants within a 6-month period. **[name]** will organize the recruitment. Our **MSc candidate #1 ([name], RD)** and our **Research Coordinator** will conduct the screening.

**10.06 Screening and Consent.** Interested individuals will call the study coordinator and be screened over the phone for eligibility using a questionnaire and be briefed on the nature of the study, treatments, and procedures. Individuals who qualify and are interested will be asked to come to the Clinical Nutrition and Risk Factor Modification Centre at the St. Michael's Hospital (study site) for an information session where they will be given the consent form. They will be permitted to take the form home so that ample time to review study procedures. Participants who provide written consent will be assigned a screening identification (ID) and will be scheduled for an in-person screening will be arranged to obtain anthropometric measures as well as questionnaire administration regarding SSB intake to confirm study qualification. The anthropometrics will include height, weight, waist circumference, and blood pressure. Automated Office Blood Pressure (AOBP) measurements at the first screening visit will be recorded in both arms unless a physical condition necessitates the use of a particular arm. The arm with the highest mean systolic measurements at screening will then be used for all subsequent AOBP assessment throughout the study. If the mean of 3 AOBP measurements in the arm with the highest systolic measurements shows systolic blood pressure (SBP)  $\geq 160$  mmHg or diastolic BP (DBP)  $\geq 100$  mmHg, then the patient will be excluded for uncontrolled hypertension [27].

Any significant results will be provided to participant's family physician for further follow-up. Those who meet all the eligibility criteria will be enrolled in the run-in phase of the study, which will last two weeks, and then be assigned a study ID. Participants will be instructed on details of the trial protocol.

**10.07 Run-in Phase.** Participants who are eligible following in-person screening will also start the  $\geq 2$ -week run-in phase. For two weeks during the run-in phase and prior to the first study visit, participants will complete a beverage log sheet. They will also be instructed on how to collect a 24-hour urine sample and fecal sample and provided kits to do so for the first study visit. The participants will be provided with their beverage log sheets for the month intervention. During the run-in phase participants will begin to log their usual beverage intake as well as asked for their beverage preference of SSB and NSB.

**10.08 Randomization.** Using the Research Electronic Data Capture (REDCap) program, the Applied Health Research Centre (AHRC) will perform the randomization with no stratification. Following successful completion of the run-in phase and following measurements taken at the first study visit, participants will be randomized into groups, of a possible six, using a blocked (Latin squares) randomization. These groups will be sequences

representing SSB, NSB and water groups. The Latin square sequences will be randomly allocated to participants with a similar number of participants allocated to each treatment sequence (**Table 2**). The randomization schedule is also created by AHRC through REDCap. The participants will only be randomized and given their study drinks once all measures from the first study visit are collected.

**Table 2: Latin square randomization for three group cross-over study.**

	Intervention Phase 1	Intervention Phase 2	Intervention Phase 3
Sequence Group 1	A	B	C
Sequence Group 2	B	C	A
Sequence Group 3	C	A	B
Sequence Group 4	B	A	C
Sequence Group 5	A	C	B
Sequence Group 6	C	B	A

*Rows represent all possible sequences and columns represent different intervention phase.*

**10.09 Intervention.** There will be three interventions: Participants will be provided with the SSB of their choice from **Table 3** (355 ml, 140kcal, 42g sugars per can), equivalent NSB (355 ml, 0kcal, 0g sugars per can), or water (355 ml, 0kcal, 0g sugars per can or bottle of still or carbonated water) to replace the amount of SSBs they usually consume ( $\geq 1$ serving/day) as determined in the run-in phase. All intervention beverages will be provided to each participant. They will be instructed to replace their usual SSBs with the study beverages while freely consuming their usual background diets. The calories of the intervention groups will not be matched to allow for “real-world” substitutions using products available on the market. They will pick up one week of their beverage assignment at the first visit of each phase and then will have the remaining three weeks of beverages delivered using an online grocery delivery service (i.e. Grocery Gateway ([www.grocerygateway.com](http://www.grocerygateway.com))). Our **MSc candidate #1 ([name], RD)** and our research coordinator will coordinate the beverage disbursements. The participants will receive relevant drinks during the intervention phase based on their group assignment. They will revert to their usual SSB intake during wash-out phase during which they will not receive any beverages from the study.

**Table 3: A full list of the three interventions and available beverages is given below.**

SSBs group – 355 ml can 42 grams of sugars	NSBs group – 355 ml can 0 grams of sugar	Water group – 355 ml bottle or can
Coca-Cola	Diet Coke (Aspartame, Acesulfame)	
Pepsi	Coca Cola Zero (Aspartame, Acesulfame) Diet Pepsi (Aspartame, Acesulfame)	
Canada Dry Ginger Ale	Diet Canada Dry Ginger Ale (Aspartame, Acesulfame)	
Schweppes Ginger Ale	Diet Schweppes Ginger Ale (Acesulfame, Sucralose)	
Mountain Dew	Diet Mountain Dew (Aspartame, Acesulfame, Sucralose)	
Sprite	Sprite Zero (Aspartame, Acesulfame)	
7UP	Diet 7UP (Aspartame, Acesulfame)	
Orange Crush	Diet Orange Crush (Sucralose)	

#### **10.10 Study visits (Week-0 and Week-4 for all 3 interventions, 6 total study visits):**

The trial will be conducted at the CFI-funded Toronto 3D Clinical Research Centre and MRI Research Unit and at the Clinical Nutrition and Risk Factor Modification Centre at St. Michael's Hospital. Each participant will receive the three interventions in random order, each separated by a ≥4-week washout. Participants will receive motivational phone calls every 2-weeks between visits to provide reminders and ensure fidelity to the protocol.

For Week-0 of first intervention only: The first visit will be scheduled upon finalizing the run-in phase.

Participants will come to the study site and their beverage logs will be checked for completion for the 2-week run-in phase, any changes required will be communicated. Participants will be notified of their randomization assignments after completing all of their baseline testing.

For all six study visits: Participants will come to the study site prior to their visit to pick up standard stool and urine collection kits as well as be instructed on how to complete a three-day diet record (3DDR) using Nutritics, a nutrition software available for use on smartphones (a paper form of the 3DDR will be available for participants who do not have access to a smartphone or prefer not to use the application). Participants will be provided with instructions for stool collection, storage, and delivery to the study centre. Stool samples will be collected in specimen containers surrounded by dry ice packs, and brought to the centre by the participants and stored in a -80C freezer. At each visit, study staff will retrieve the stool sample, the 24-hour urine collection, and beverage logs. Subjects will come in to the study site in a 10 to 12-hour fasted state. They will be instructed to maintain the same dietary and exercise patterns the evening before each test and consume a minimum of 150g of carbohydrate each day over the three days prior to the test. To ensure that these instructions are followed, participants will be provided with examples of what constitutes 150g of carbohydrate. Their weight, waist circumference, and blood pressure will be measures. A fasting blood sample for primary, secondary, and exploratory outcomes (including glucose, insulin, lipid panel, ALT and other liver enzymes, and other markers of glucose control, biomarkers of adherence, and other biomarkers of cardiometabolic risk) will be taken by an intravenous nurse. A standard protocol will be followed for the administration of a 2-hour 75g-OGTT.

Participants will have a catheter inserted into a forearm vein by the nurse, secured by tape, and kept patent by saline. Two baseline samples will be obtained in the fasting state at 0-min. A 75g OGTT meal (GlucoDex 75g, Rougier Pharma Mirabel, QC, Canada) will then be administered with instructions to consume it over exactly 5 min at a constant rate using a timer. Additional blood samples will be drawn at 30, 60, 90, and 120 min after the start of the test, at the end of the test the nurse will remove the catheter. Breakfast will be prepared at the study site kitchen and provided to the participants after the OGTT. Staff will also administer case report forms and questionnaires which will include information on diet (cravings, hunger and fullness), physical activity,

medication changes, and symptoms. The study dietitians will review the 3DDR with participants. For the 30 participants who will participate in the imaging portion of the study, a 1H-MRS scans will be conducted in the CFI-funded Toronto 3D Centre MRI research unit at St. Michael's Hospital. The 1H-MRS will be performed to measure ectopic fat in liver and calf muscles (**Table 4**). Once all measures have been collected, the participant will be provided the intervention. For week-0 of all 3 interventions, participants will be given 1 week's worth of beverages to take home; the beverages for the remaining 3 weeks will be delivered using an online delivery service (Starhawk express (<https://www.starhawkexpress.com/>))). They will also be provided with their beverage log sheets for the month

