## 9. HYPOTHESIS

[figure not shown]
1. Replacing SSBs with NSBs or water will change the diversity of gut microbiome after four weeks in regular SSB drinkers.
2. Replacing SSBs with NSBs or water will increase glucose tolerance after four weeks in regular SSB drinkers.
3. Replacing SSBs with NSBs or water will decrease body weight, reduce blood pressure, improve glucose and insulin regulation, decrease blood lipids, decrease ectopic fat, decrease liver fat, decrease body adiposity, and improve diet quality after four weeks in regular SSB drinkers.

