## 10. METHODS

**10.01 Trial Design.** We will conduct a single-centre, open label, randomized controlled crossover trial with three four-week intervention phases (SSB, NSB, water) comparing the effect of replacing SSBs with NSBs or water on the gut microbiome and glucose tolerance. A cross-over design was selected due to the high inter-individual heterogeneity in gut microbiome [25]. Prior to randomization, participants will undergo a ≥2-week run-in phase

to gather data on SSB consumption prior to study start. Each participant will then act as their own control receiving the 3 interventions in random order, each separated by a  $\geq 4$ -week wash-out phase (Figure 1). We will collect fecal samples from participants and conduct Oral Glucose Tolerance Tests (OGTTs) before the start and at the end of each intervention for gut microbiome analysis and glucose tolerance. All study visits will occur in Toronto at the Clinical Nutrition and Risk Factor Modification Centre at St. Michael's Hospital. The microbiome analysis and the objective biomarkers of SSBs assays will be performed at the Department of Nutritional Sciences, University of Toronto; plasma glucose analysis will be performed at the Banting and Best Diabetes Center (BBDC), University of Toronto; plasma insulin analysis and other blood analyses (for a selected sample using a multiplex kit for adiponectin, adiponisin, C-Peptide, Ghrelin, GIP, GLP-1, Glucagon, Insulin, leptin, PAI-1, Resistin and Visfatin) will be conducted at the Guelph Research and Development Centre, Ontario, Canada. Lipid analyses will be performed at St. Michael's Hospital Core Lab.

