#### Questionnaires

**Dietary Assessment.** Participants will be asked to fill out a weighed 3DDR using Nutritics, a nutrition software available for use on smartphones. The 3DDR will consist of two non-consecutive weekdays and one weekend day during the run-in phase and during the last week of each intervention. If participants do not have access to a smartphone, a paper form of the 3DDR will be provided. Participants will also be provided with scales to insure the accuracy of the record. Registered dietitians will instruct and review 3DRDs with participants. The 3DRDs will be used to evaluate changes in diet quality and will be analyzed by using Nutritics. Food cravings, hunger, and satiety will be assessed using modified Corby Martin's Questionnaires [48].

**Behavior of beverage consumption** will be assessed with a product consumption questionnaire. This will be done at the last visit for the participants that are still enrolled in the study and via telephone or email for the participants that have completed the study.

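### End-of-phase diet records nearly always include days on which participants are told to eat at least 150 g carbohydrate, a floor that can act differently by arm

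*Combined protocol and SAP*

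**What the plan says.** Section 10.01 schedules OGTTs "before the start and at the end of each intervention". Section 10.10 opens its procedures with "For all six study visits: Participants will come to the study site prior to their visit" and, under that heading, tells participants to "consume a minimum of 150g of carbohydrate each day over the three days prior to the test". They also receive examples of what 150 g looks like, so that the instruction is followed.

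Section 10.13 (Dietary Assessment) sets the diet record on "two non-consecutive weekdays and one weekend day during the run-in phase and during the last week of each intervention". Section 10.11 lists diet quality, taken from these records, among the exploratory outcomes. It also appears in Objective 3 and in Hypothesis 3, which expects replacement of SSBs to "improve diet quality after four weeks in regular SSB drinkers". Section 10.09 has participants replace their SSBs "while freely consuming their usual background diets".

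Table 4 marks the diet record at Week 0 and Week 4 of phase 1 and at Week 4 of phases 2 and 3. Its run-in column is blank for this item.

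**The concern.** The three preparation days lie inside the week from which the end-of-phase record must be drawn, and nothing in the plan keeps the record off them. The record is meant to show what people eat when SSBs are removed and the rest of the diet is left free. On a preparation day the diet is not entirely free.

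An instruction common to all phases would cancel in a crossover if it acted equally in each. This one need not. In the SSB phase the beverage itself counts towards the 150 g; in the NSB and water phases the whole amount must come from elsewhere in the diet. Any distortion therefore follows the treatment, and the within-person comparison does not remove it. At stake is how the diet-quality contrast, and any statement about compensatory eating, is interpreted.

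**Working it through.** The plan gives no figure on this point, so there is none to reproduce.

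**Inputs from the documents.** Record: two non-consecutive weekdays plus one weekend day, last week of the phase (10.13). Preparation: days -3, -2 and -1 before the OGTT, at least 150 g/day (10.10). SSB can: 42 g sugars; NSB and water: 0 g (10.09, Table 3).

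**Assumptions.** Visits fall Monday to Friday; the last week is days -7 to -1 before the visit; every permitted set of days is equally likely.

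**Step 1: overlap.** All permitted sets were listed for each visit weekday.

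| Visit | Permitted sets | Sets with at least one preparation day | Mean preparation days (of 3) |
|---|---|---|---|
| Mon | 12 | 12 | 1.50 |
| Tue | 14 | 14 | 1.57 |
| Wed | 14 | 13 | 1.36 |
| Thu | 14 | 14 | 1.14 |
| Fri | 14 | 12 | 1.00 |
| All | 68 | 65 (95.6%) | 1.31 |

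Of the 68 sets, 3 contain no preparation day, 41 contain one, 24 contain two and none contains three. The three that avoid overlap are Wed+Fri+Sat for a Wednesday visit, and Fri+Mon with Sat or Sun for a Friday visit.

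Sensitivity: 59/60 if Friday and Monday count as consecutive; 39/39 if all three days must be non-consecutive; 36/36 with a six-day window; 88/92 with visits on any weekday. The range is 95.6% to 100%.

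**Step 2: what the floor can add.** Let U be usual carbohydrate including SSB and c the cans per day. With no other compensation and full compliance, the extra on a preparation day in the NSB or water phase is max(0, 150 - (U - 42c)). In the SSB phase it is max(0, 150 - U), which is 0 for every U below. U is assumed; the documents do not give it.

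| U (g/day) | 1 can | 2 cans | 3 cans |
|---|---|---|---|
| 200 | 150 - 158 < 0, so 0 | 150 - 116 = 34 | 150 - 74 = 76 |
| 250 | 0 | 150 - 166 < 0, so 0 | 150 - 124 = 26 |
| 300 | 0 | 0 | 150 - 174 < 0, so 0 |

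At 1 can the floor binds in the NSB and water phases only if U is below 150 + 42 = 192 g/day.

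**Step 3: grams in the record average.** Multiply by mean preparation days / 3, that is 1.00/3 to 1.57/3. For 34 g: 11 to 18 g/day. For 76 g: 25 to 40 g/day. For 26 g: 9 to 14 g/day.

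**Step 4: an earlier window.** With days -10 to -4, the permitted sets number 14, 12, 12, 12 and 14 for Monday to Friday visits. All 64 are free of preparation days, because the window ends on day -4.

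**The case against.** The strongest reply is that overlap is not bias. The instruction is a minimum, so someone who already eats 150 g or more without the SSB need change nothing, and a preparation day may be an ordinary day. This stands. A reader might infer that the record, as scheduled, partly measures the OGTT instruction in everyone. The documents do not support that, because they give no usual carbohydrate intake. The non-zero cases above need SSBs to supply a large share of all carbohydrate: 84/200 = 42%, 126/250 = 50% and 126/200 = 63%. Entry requires only one serving a day, and at one can and 200 g/day the effect is zero. The entry criterion sets no upper limit, however, so heavier drinkers are eligible.

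A reader might also infer that the baseline record contains fewer preparation days than the later ones, which would bias change from baseline. If days were picked at random over a 14-day run-in, 55-62% of baseline records would include one, against 86-100% (by visit weekday) at the end of a phase. But the plan does not say that days are picked this way. Section 10.13 allows any run-in days, while Table 4 ties the record to phase 1 Week 0; a record kept close to that visit would overlap about as much. This asymmetry is uncertain.

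Finally, the arithmetic concerns grams of carbohydrate. No effect on a diet-quality measure has been derived, and the outcome is exploratory, without false-discovery control. Nothing here reaches the two primary outcomes.

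**Conclusion.** The overlap is real and follows from the plan's own timing rules: 95.6% to 100% of permitted end-of-phase records contain one or two preparation days. Where the 150 g floor binds, it can raise recorded food carbohydrate in the NSB and water phases and not in the SSB phase, and the crossover does not cancel this.

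The size cannot be computed from the documents. Under the assumed intakes it runs from 0 (any case at 300 g/day up to 3 cans; 1 can at 200 g/day) to about 25-40 g/day in the record average (3 cans at 200 g/day), so it is concentrated in heavier drinkers with modest total intake. It rests on full compliance and no other compensation. It touches only the exploratory diet-quality outcome and the description of diet. This is a minor point, worth acting on because the change is cheap.

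**What to change.** In sections 10.10 and 10.13, state that every diet record, run-in and end-of-phase, is kept on days -10 to -4 before the visit. Any seven consecutive days hold a permitted set, so the rule of two weekdays and one weekend day is kept. Applying the same window to the run-in record also settles the uncertainty about baseline. The OGTT preparation is left as it is.

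Cost: no extra records, visits or staff in themselves, but record instructions must reach participants by day -10. Section 10.10 gives them at kit pick-up, at an unstated time before the visit, so the pick-up may have to move or the instructions be sent separately. The record would describe late week 3 to early week 4 rather than the final days of the phase, and would no longer show intake on the preparation days.

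For records already collected, flag the preparation days and repeat the diet-quality analysis without them. Most such records will then rest on one or two days, so this serves as a sensitivity analysis only.

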**Washout (2 x 4 weeks):**

At the end of week-4 for the first two interventions, the wash-out phase of ≥4 weeks will start for which participants will be asked to revert back to their usual beverage intake. Participants will be given a beverage log to complete over this four-week phase. No beverages will be provided by the study site during the wash-out phase. The study coordinator will call the participants near the middle and near the end of each phase to remind them of their group assignment and the next study visit. Reminders will also be sent via email.

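### Only the phase 1 baseline is protected from knowledge of the arm; as most naturally read, the plan lets participants know the next beverage before Week 0 of phases 2 and 3

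*Combined protocol and SAP*

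**What the plan says.** **Randomisation (10.08).** After run-in and the first-visit measures, "participants will be randomized into groups, of a possible six, using a blocked (Latin squares) randomization". The protocol then defines the term: "These groups will be sequences". The phase 1 baseline is explicitly protected: "The participants will only be randomized and given their study drinks once all measures from the first study visit are collected".

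**Disclosure (10.10).** The paragraph that opens "For Week-0 of first intervention only: The first visit will be scheduled upon finalizing the run-in phase" ends: "Participants will be notified of their randomization assignments after completing all of their baseline testing". No matching step is written for phases 2 and 3.

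**Handover (10.10, all six visits).** "Once all measures have been collected, the participant will be provided the intervention". This governs when the drink is supplied.

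**Wash-out (10.10).** When phases 1 and 2 end, "the wash-out phase of ≥4 weeks will start for which participants will be asked to revert back to their usual beverage intake". Under the same heading the coordinator calls participants "near the middle and near the end of each phase to remind them of their group assignment and the next study visit", with email reminders as well.

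**Use of the Week-0 data.** Stool, OGTT, weight, waist and blood pressure are taken at Week 0 of every phase (Table 4). Section 10.11 describes the outcomes as changes. Section 10.02 states that participants cannot be blinded.

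**The concern.** Holding back randomisation until the first-visit measures are complete keeps knowledge of the arm from affecting that baseline. In a crossover measured as change within each phase, the Week-0 values of phases 2 and 3 need the same protection, and the plan does not write it.

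In wash-out, participants buy their own drinks. Someone who knows that water or diet soda comes next may switch early, or may drink more SSBs while still free to. Someone who knows that SSB comes next has little reason to change. Behaviour of this kind depends on the coming arm, so balancing the order across sequences does not cancel it. Blinding the laboratory and the statistician does not help either, because the change happens before the sample is taken. The Week-0 value would then carry part of the arm's effect, or a rebound against it, and the change score would be off by that amount.

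**Working it through.** The plan gives no figure for disclosure or anticipation, so there is none to reproduce. The check compares the passages and counts visits.

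**1. What a participant can know, from the six sequences in 10.08** (ABC, BCA, CAB, BAC, ACB, CBA).
- Whole sequence disclosed at visit 1: the next beverage is known before Week 0 of phase 2 and of phase 3 in 6 of 6 sequences.
- Only the current beverage disclosed: after phase 1, two sequences remain (A: ABC or ACB; B: BCA or BAC; C: CAB or CBA), so the phase 2 drink is one of two. After phase 2, exactly one sequence remains, so phase 3 is known by elimination.

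**2. What a wash-out call about the group assignment could convey.** No study beverage is in use at that time. The rows about a single arm assume that visit 1 disclosed only the first beverage.

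| Content of the call | Phase 2 drink known before Week 0? | Phase 3 drink known before Week 0? |
|---|---|---|
| The sequence (the 10.08 definition of a group) | Yes | Yes |
| The coming arm | Yes | Yes |
| The arm just finished | No | Yes, by elimination |
| Usual intake and visit date only | No | Yes, by elimination |

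The first row follows the protocol's own definition. The third would serve little purpose in a call that also announces the next visit. The fourth is not what the sentence says.

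**3. Does the handover rule close the gap?** Section 10.08 delays the allocation itself, so at the first visit there is nothing to know. The rule for all six visits delays only the supply of drinks. By phases 2 and 3 the allocation already exists, and no sentence keeps it from the participant.

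**4. Is there time for it to matter?** A wash-out of 4 weeks is 28 days, so a call near the middle leaves about 28 / 2 = 14 days before Week 0. Section 10.04 cites diet-related changes in gut taxa within 5 to 7 days. Fourteen days is at least twice that.

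**5. How many visits?**
- All Week-0 visits, if all 81 attend every one: 81 × 3 = 243.
- Phases 2 and 3: 81 × 2 = 162, the maximum exposed.
- Phase 3 only, which remains deducible after the fix: 81 × 1 = 81.
- With the 60 participants on whom power is based: 120 of 180, falling to 60 of 180.

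The share falls from two thirds to one third in either case.

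**6. Would the plan detect it?** Beverage logs run through wash-out, and 24-hour urine is collected at each Week 0. Every diet drink in Table 3 contains acesulfame or sucralose, both of which are assayed, so an early switch to one of these could show. Stopping SSBs would tend to show in urinary fructose. However, Section 11 specifies no comparison of these measures by upcoming arm. Table 4 schedules no three-day diet record at Week 0 of phases 2 and 3, and 10.13 agrees, although the all-visits text in 10.10 reads otherwise.

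**The case against.** The strongest reply is that no sentence says participants are told their whole order. The word *group* also means a single arm: Table 3 heads its columns that way, and 10.08 itself speaks of SSB, NSB and water groups. The plural *assignments* may simply follow from the plural *participants*. In an intervention phase, a reminder of the assignment naturally means the current drink. This much stands: prior knowledge of the arm is the most natural reading, not a stated fact, and it would be wrong to say that the wash-out call could mean nothing else.

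The safeguards also count. Participants are asked to return to usual intake and keep a log. They are asked to hold diet and exercise patterns the evening before each test and to meet a carbohydrate minimum for three days. Those planning dietary changes are excluded. Urine biomarkers are collected. These lower the risk and make some of it visible. A reader might infer that the wash-out is undone, and the documents do not support that.

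A reader might also assume some fraction of early effect and compute a loss in the planned iAUC difference. The documents give no such fraction. The direction is open, since early switching and extra SSB intake pull opposite ways. The planned difference is water against NSB, and cutting SSBs early before either arm would largely cancel in that contrast.

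Finally, the fix is partial, and the trial appears to be under way: 10.04 reports recruitment in the past tense and 10.13 mentions participants who have finished. Both points stand as limits on the fix. They do not justify leaving the later baselines unprotected.

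**Conclusion.** The concern holds as a design risk. The rule of measuring first and disclosing afterwards is written for phase 1 only. Followed as most naturally read, the plan reveals the next beverage before the Week-0 measures of phases 2 and 3. The exposure is at most two of the three Week-0 visits per participant (162 of 243 under full attendance by all 81). No bias in the effect estimates is shown, and neither its size nor its direction can be derived from the documents.

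The conclusion rests on two assumptions: that *group assignment* carries the 10.08 meaning or names the coming arm, and that some participants would act on the knowledge. If the calls name only the arm just finished, and visit 1 discloses only the first drink, the phase 2 baseline is already protected and only the wording needs repair. Because the change costs little and the Week-0 values feed the primary outcomes, it should be made and not left as a matter of interpretation.

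**What to change.** **Conduct.** Keep the REDCap sequence as planned, but release only the current phase's beverage to the participant, once that phase's Week-0 stool, OGTT and anthropometry are complete. State in 10.08 and 10.10 that this applies to all three Week-0 visits. Limit wash-out calls and emails to usual intake, the beverage log and the next visit date.

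**Analysis.** For participants already told their order, prespecify a sensitivity analysis of the primary outcomes using end-of-phase values, or using the phase 1 baseline in place of the later ones. Compare wash-out logs and Week-0 urine biomarkers by upcoming arm. State in Section 11 how the Week-0 values of phases 2 and 3 enter the mixed models.

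**Cost.** The change needs amended wording and a revised call script. Drinks are already handed over after the measures, and brand preferences are collected at run-in (10.07), so nothing operational requires early disclosure. Three limits remain: phase 3 stays deducible, so the gain is mainly for the phase 2 baseline; participants who know their order are helped only by the analysis; and a mid-trial change mixes two disclosure regimes, so its date should be recorded.
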